Delay Discounting (DD)	Reward, Impulsivity, Restraint	16 min	MFG, anterior insula, ACC, PCC, MedFG
Working Memory (WM)	WM, WM Cognitive Persistence	8 min	MFG, IPL, SMA
Inhibitory Control (IC)	Inhibitory Control	12 min	
Rest	Default Network	6 min	PCC, MedFG

Abbreviations: Middle frontal gyrus (MFG), anterior insula (AI), anterior cingulate (ACC), posterior cingulate (PCC), medial frontal gyrus (MedFG), inferior parietal lobule (IPL), supplementary motor area (SMA), ventral striatum (VS).

Delay Discounting Paradigm. This paradigm will be presented to examine decision-making for smaller immediate rewards versus larger delayed rewards. Thus, this task will assay impulsive choice preferences and the relative activity of both motivational drive and inhibitory control prior to entering buprenorphine treatment. Using an event-related design, participants make choices between smaller immediate rewards or larger delayed rewards over 72 trials (e.g., “Would you rather have \$25 today or \$35 in 29 days”). Each item has a temporal discounting function and the overall array of responses permits calculation of an individuals’ discounting level.

Working Memory Paradigm. The 2-Back version of the n-Back has been widely used in fMRI experiments as a WM challenge (i.e., a construct that refers to the process of short-term storage and management of information). This task challenges persistence during a sustained cognitive set since information is constantly maintained and updated over six 45s blocks of time. During the 2-Back WM challenge a series of 15 consonants are presented visually, one every 3000 ms. Participants make a yes/no response following each consonant - whether it is the same as, or different from, the consonant presented two earlier. Each consonant block contains 33% stimulus-target consonants pairs, which randomly overlap (e.g., F, N, B, **N**, **B**, K, **B**, **K**, N...). The *0-Back task* (a control task for the 2-Back) will include nine consonants presented at the standard 3000 ms rate. Subjects respond "yes" when a predetermined target consonant appears and "no" for other consonants. In total, there will be two runs of six 2-Back blocks each, requiring 4.8 minutes to complete (including control blocks). Three blocks of the 0-Back and three blocks of the rest will be included in each run. Accuracy and reaction time will be used as dependent measures of cognitive performance.

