Aim 1. 1) Altered response to targeted challenges. These hypotheses will be tested using independent samples t-tests using mean task-associated activity in each ROI (listed in Table 1) as the dependent measure. For contrasts of cognitive persistence during the WM challenge, a linear mixed effects model for repeated measures will be conducted that allows estimates of contrasts of group over time and interactions. Parallel contrasts of behavioral measures will also be conducted for each task. 2) Disorganization of neural networks. Functional connectivity analyses will be conducted to determine the strength of relationships between the nodes of each network listed in Table 1. These will be converted to z-scores using Fisher's transformation and contrasted across groups using independent samples t-tests. 3) Compensatory mechanisms. Compensatory overactivation will be assessed using voxel-wise independent samples t-tests. Voxel threshold will be $<.05$ corrected for multiple comparisons. We expect more recruitment of regions outside of the *a priori* ROIs among the lapsers during all fMRI paradigms. Although assessed qualitatively due to a lack of *a priori* spatial extent, we will count both clusters of significant activity and total volume of significant activity outside of *a priori* ROIs in order to perform exploratory group contrasts. Compensatory underactivation will be assessed using independent samples t-tests of mean task-related responses (i.e., DD, WM, WMCP, IC) in regions identified as the DN in the independent functional connectivity analyses of the resting state imaging run. We expect that while fMRI predictors for lapse and relapse will be related, they will not be identical. We plan primary analyses to separately examine both lapse and relapse. Although they are strongly associated, this permits identification of differential relationships between each and fMRI challenges, if present. Prediction and prevention of relapse is the most important goal of this line of research; however, we still include lapse, since it has been used as the outcome measure in most relevant studies.

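### The voxel-wise group t-test for compensatory overactivation in Aim 1 cannot tell extra recruitment in lapsers from weaker deactivation, so reduced suppression could be reported as compensation

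*SAP*

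**What the plan says.** Aim 1 in section C4 of the SAP names three markers. The third, compensatory mechanisms, has two parts.

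- **Overactivation.** "Compensatory overactivation will be assessed using voxel-wise independent samples t-tests", with the voxel threshold at .05, "corrected for multiple comparisons". The correction method and sidedness are not given. The hypothesis is directional: "We expect more recruitment of regions outside of the *a priori* ROIs among the lapsers during all fMRI paradigms". As an exploratory addition, "we will count both clusters of significant activity and total volume of significant activity outside of *a priori* ROIs".
- **Underactivation.** "Compensatory underactivation will be assessed using independent samples t-tests of mean task-related responses (i.e., DD, WM, WMCP, IC) in regions identified as the DN", those regions being taken from the resting run.

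Table 1 of the protocol lists MFG, IPL and SMA as ROIs for the working memory task (domains "WM, WM Cognitive Persistence"). For delay discounting it lists "MFG, anterior insula, ACC, PCC, MedFG". For the resting run, whose domain is the default network, it lists PCC and MedFG.

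Neither document requires the lapsers' own response to be above zero before a difference is called overactivation. Neither says how a default-network cluster with lapsers above nonlapsers is to be labelled.

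**The concern.** The hypothesis is about recruitment: lapsers bring in regions that nonlapsers do not. The null hypothesis tested is that the two groups have equal mean response at a voxel. That null is false when lapsers activate a region and nonlapsers do not. It is equally false when neither group activates it and nonlapsers merely suppress it more.

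Only the first case is extra recruitment. The second is reduced suppression, which is a different finding and arguably a contrary one. As written, both would emerge from the same test under the label of compensatory overactivation. What is at stake is the interpretation of one of the three Aim 1 markers, which C4 evaluates in stable use and in withdrawal, and for lapse and relapse.

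**Working it through.** **Inputs from the documents.** The sample is 72 (protocol C1). About 20% are expected to be lost to analytic exclusions (protocol C3, FMRI), leaving 72 × 0.8 = 57.6. Groups are formed by lapse within a week or, failing that, by median split (SAP C4), so a near-even split is used here. The documents give no effect size, SD or power figure, so there is no stated figure to reproduce.

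**Step 1: what the test responds to.** The statistic is t = (mean L − mean N) / [s √(1/n_L + 1/n_N)]. Its noncentrality is d √[n_L n_N / (n_L + n_N)], where d is the difference in SD units. The level of either mean does not enter. With 29 v 29 and d = 0.8, the noncentrality is 0.8 × √(841/58) = 0.8 × 3.808 = 3.05, whether the means are +0.8 v 0, 0 v −0.8 or −0.2 v −1.0.

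**Step 2: one voxel, 40,000 simulated trials, SD 1.** Share of runs with lapsers significantly above nonlapsers:

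| True means (lapser v nonlapser) | two-sided .05 | two-sided .001 |
|---|---|---|
| +0.8 v 0 (recruitment) | 84.7% | 34.7% |
| −0.2 v −1.0 (weaker deactivation) | 85.1% | 34.8% |
| 0 v −0.8 (no deactivation) | 84.9% | 34.7% |

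The noncentral-t power at d = 0.8 is 0.849 and 0.348, in agreement. For d from 0.5 to 1.2 it runs from 0.465 to 0.994 at .05 and from 0.070 to 0.855 at .001.

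**Step 3: a whole search, with a candidate rule.** Assumptions: 28 v 29; 200 search units; two-sided family-wise 5% by Bonferroni (critical t = 3.917 on 55 df); 20 units carry the effect, with intercorrelation 0.5. The table gives the chance of at least one lapser-greater unit labelled overactivation. Rule A also requires the lapsers' own mean to be above zero at one-sided 5%, uncorrected. Rule B requires the same at a search-wide corrected level.

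| Lapser v nonlapser mean in the 20 units | As planned | Rule A | Rule B |
|---|---|---|---|
| −0.5 v −0.5 (no difference) | 2.6% | 2.1% | 1% or less |
| −0.3 v −0.8 | 27% | 3% | 1% or less |
| −0.2 v −1.0 | 75% | 7% | 1% or less |
| −0.5 v −1.5 | 94% | 2% | 1% or less |
| 0 v −0.8 | 75% (same difference as −0.2 v −1.0) | 32% | about 1% |
| +0.6 v −0.2 (true activation) | 75% | 75% | 63% |
| +0.8 v 0 (true activation) | 75% | 75% | 74% |

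Without a group difference the expected rate in this direction is 2.5%. The as-planned figures move with the assumed number of units. For −0.2 v −1.0 the rate is 87% with 50 units and 56% with 1,000; for −0.3 v −0.8 it is 45% and 13%.

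**Step 4: where this can occur.** Set Table 1 beside the SAP's search region. Read task by task, PCC and MedFG are outside the working memory ROIs and so are searched. For delay discounting both are a priori ROIs and are not. Read as the union of all Table 1 ROIs, both drop out for working memory too. Only default-network regions that the resting run adds, or other deactivating regions, then remain exposed, and the documents name none.

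**The case against.** Several points against the concern are sound, and they limit it.

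- **The counts.** A reader might infer that weaker deactivation would inflate the cluster and volume counts. The documents do not support this. The counts are of significant activity and feed group contrasts, which suggests activity counted within each group or participant. If positive activity is counted, a voxel at −0.2 SD in lapsers adds almost nothing (0.1% at .05). If either sign is counted, weaker deactivation lowers the lapsers' count (17.9% v 99.9% of voxels).
- **Either sign supports compensation.** A reader might infer that no default-network difference in working memory could count against the marker. That goes too far. The SAP does not say which group should underactivate, and it gives no rule by which one sub-test establishes the marker. If lapsers are the group expected to underactivate, a higher lapser response contradicts that in the dedicated default-network test.
- **Expected deactivation.** The plan nowhere states that these regions fall during the tasks. The negative means above are assumptions.
- **The simulated rates.** They are the power to detect assumed real differences, not error rates derived from the documents.
- **Stakes.** The a priori ROI analyses are the primary method, overactivation is described as qualitative, and Aim 2 is specified per ROI.

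What survives is the central point: the voxel-wise test cannot make the distinction that its label claims, and nothing else in the overactivation analysis makes it.

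**Conclusion.** The concern holds for the voxel-wise t-test in Aim 1, part 3. That test detects weaker deactivation as often as true recruitment of the same size: 85.1% against 84.7% for one voxel at 0.8 SD and .05. This equality follows from the form of the statistic and needs no assumption about the data. How often a misleading result would arise does depend on assumptions: 27% to 94% over the three whole-search scenarios with 200 units, for differences of 0.5 to 1.0 SD.

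Exposure is greatest in working memory if the search region is defined task by task, because PCC and MedFG are then searched. It is narrower if the union of Table 1 is meant, and the SAP should say which. The consequence is a mislabelled finding on the third marker. The primary ROI tests and Aim 2 are untouched, and the documents do not show that the cluster and volume counts are biased.

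**What to change.** In Aim 1, part 3, call a lapser-greater cluster overactivation only where the lapsers' own task response is significantly above zero at a threshold corrected for multiple comparisons. Name the contrast that defines zero: for working memory, 2-Back minus the 0-Back control, since that task also contains rest blocks. Report all other lapser-greater clusters, including those in the default-network regions from the resting run, as reduced deactivation and not as compensation. Apply the same rule to the relapse grouping. State whether the a priori ROIs are those of the task or all those in Table 1.

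The positivity threshold should be corrected. An uncorrected one-sided 5% rule still labelled 32% of runs as overactivation when lapsers were at zero and nonlapsers at −0.8; the corrected rule brings this to about 1%.

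The default-network mask need not be removed from the search. Removing it would also control the problem there, but it would discard true recruitment in those regions (detection falls from 75% to about 2% for +0.6 v −0.2).

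The cost is a few sentences and one extra mask, with no new data. Power for weak true activation falls: 75% to 63% for +0.6 v −0.2, and 75% to 74% for +0.8 v 0, under the same assumptions.

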Neuroimaging predictors of relapse during treatment for Opiate dependence
NCT: 02696096
June 22, 2017

C4. Data Analysis

A priori ROI analyses will be our primary method for quantifying task-related effects for hypothesis testing, while analyses involving the functionally defined ROIs will serve to validate our *a priori* findings.

We will test hypotheses using lapse as the grouping variable and then with relapse. Three markers (altered response, disorganized response, and compensatory mechanisms; see Aim 1) will be evaluated in both the stable opiate use state and during opiate withdrawal.

We will compare lapsers and nonlapsers on pre-quit behavioral and fMRI measures hypothesized to predict lapse (Aim 1) followed by application of Cox regression models predicting time to relapse among the full sample to determine if neuroimaging measures provide additional utility in predicting lapse (Aim 2). Although Aim 1 hypotheses are designed to be tested as group contrasts based on lapse within 1 week of quitting, we will group by median split of time to lapse if this results in unacceptable differences in group size.

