Aim 2. For each targeted relapse-risk domain, comparisons of behavioral and fMRI markers will be examined per ROI using logistic regression (lapse) and Cox proportional hazards survival models predicting time to relapse conditional on planned covariates including gender, age, social support, self-efficacy, *comorbid alcohol and drug use*, and mood. The unique explanatory contribution of fMRI responses will be evaluated by comparing a full model (including fMRI response, behavioral data acquired during the fMRI challenges, and covariates) to a reduced model, which includes only the behavioral data and covariates.

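### The SAP credits its separate lapse and relapse analyses with revealing predictors that differ between the outcomes, but plans no comparison between them (minor)

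*SAP*

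**What the plan says.** All the relevant text is in SAP section C4.

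- Under Aim 1 the SAP states an expectation: "We expect that while fMRI predictors for lapse and relapse will be related, they will not be identical". It then sets the approach, "We plan primary analyses to separately examine both lapse and relapse", and gives the reason: "Although they are strongly associated, this permits identification of differential relationships between each and fMRI challenges, if present".
- The same paragraph ranks the outcomes: "Prediction and prevention of relapse is the most important goal of this line of research". Lapse is kept because most of the relevant earlier studies used it.
- Aim 1 runs its group contrasts by lapse and then by relapse. Lapse means lapse within one week of quitting, with a fallback: "we will group by median split of time to lapse if this results in unacceptable differences in group size".
- Aim 2 models the outcomes "using logistic regression (lapse) and Cox proportional hazards survival models predicting time to relapse", with covariates. It compares a full model with one that omits the fMRI response.
- The three markers "will be evaluated in both the stable opiate use state and during opiate withdrawal", so every contrast is repeated over two states.

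**The concern.** The SAP predicts a difference between the outcomes and names separate analysis as what makes that difference identifiable. Two separate analyses show whether a marker is associated with lapse and whether it is associated with relapse. They do not show whether the two associations differ. With no direct comparison and no criterion for calling a predictor differential, the easiest basis for such a claim is that a marker is significant for one outcome and not for the other. With correlated outcomes, a modest sample and moderate power, that pattern arises fairly often when the true associations are the same. What is at stake is any later statement that an fMRI marker is specific to lapse or to relapse.

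**Working it through.** **Step 1: does any planned analysis cross the two outcomes?** Going through C4:

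| Planned analysis | What it contrasts | Compares lapse with relapse? |
|---|---|---|
| ROI, connectivity, voxel-wise and default-network t-tests | Two groups within one outcome | No |
| Mixed model for working-memory persistence | Group over time, and their interaction | No |
| Logistic regression (lapse) | Marker within lapse | No |
| Cox regression (relapse) | Marker within time to relapse | No |
| Full against reduced model | Added value of fMRI over behaviour and covariates, within one outcome | No |

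The two nearest candidates, the mixed-model interaction and the full-against-reduced comparison, answer other questions.

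**Step 2: could the Aim 2 coefficients be compared by eye?** No. In simulated data with an identical hazard ratio of 1.5 for both outcomes (log 1.5 = 0.41), n = 58 and six covariates, the median logistic coefficient was 0.64-0.67 and the median Cox coefficient 0.45-0.46. The ratio runs from 0.64/0.46 = 1.39 to 0.67/0.45 = 1.49. A gap of that size appears with no true difference. Event rates and time distributions were assumed.

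**Step 3: how often would two Aim 1 t-tests disagree under identical true effects?** The plan gives no figure to reproduce.

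Inputs:
- Sample: 72 (Protocol C1), less approximately 20% fMRI exclusions (Protocol C3, FMRI): 72 x 0.80 = 57.6, about 58.
- Assumed, because the documents give none: standardised effect d, event rates, lapse-relapse phi, and two-sided 0.05 for the ROI tests. The 50/50 split is roughly what the median-split fallback would give for lapse.

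Simulated proportion significant for exactly one outcome (20,000 runs per cell, n = 58, 50/50 splits, equal d):

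| True d for both outcomes | phi 0.75 | phi 0.9 |
|---|---|---|
| 0 | 6.4% | 4.0% |
| 0.5 | 23.1% | 13.9% |
| 0.65 | 21.7% | 13.2% |
| 0.87 | 10.9% | 6.9% |

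**Step 4: cross-checks.**
- Normal approximation, n = 57. Each test statistic has mean d x sqrt(n/4): 0.5 x sqrt(57/4) = 1.89 and 0.8 x sqrt(57/4) = 3.02, with single-test power of about 47% and 86%. At a correlation of 0.9 between the statistics, exactly one is significant in 14% (d = 0.5) and 8% (d = 0.8); at 0.7, in 25% and 14%. A direct test, (z1 - z2)/sqrt(2(1 - r)), rejects in 5% throughout.
- Lapse and relapse as two cut-points on one latent severity (phi 0.65-0.67): 19-28% discordant where each test has roughly 20-80% power, and 7-8% with no effect.

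**The case against.** The sentence at issue is a hedged rationale for analysing two outcomes, not an aim or a hypothesis with a decision rule. Aims 1 and 2 can be answered in full as written. That is correct, and it is why the point is minor.

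A reader might infer that the SAP intends to treat significance for one outcome only as proof of a difference. The documents do not say so. They give neither a rule for such a reading nor a rule against it, so this is an open gap and not a planned misuse.

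A reader might also choose a weak lapse-relapse association to make the problem look larger: at phi 0.4 the same simulation gives 38.0% discordance at d = 0.5. The SAP calls the outcomes strongly associated, so the lower figures are nearer to what it describes.

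Nor can one count expected false claims from Table 1 of the Protocol. A row such as "MFG, anterior insula, ACC, PCC, MedFG" lists ROIs, but the Inhibitory Control row shows none in the available text, possibly lost in extraction. Connectivity and default-network contrasts add further tests.

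Finally, a direct test would often have low power. This stands as a cost, but it does not rescue the alternative: discordant p-values cannot reliably separate effects that a direct test cannot separate.

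**Conclusion.** The point holds as a gap between a stated property of the plan and the analyses planned; it rests on the text of C4 and not on the simulations. The simulations only show its scale: about 7-14% discordance at phi 0.9 and 11-23% at phi 0.75 for identical effects of d 0.5 to 0.87, with every input except the sample size assumed.

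It would be wrong to conclude that the lapse or relapse analyses are invalid, or that the goal ranked first is compromised. Each analysis answers its own within-outcome question. Only a claim that a marker predicts the two outcomes differently would be unsupported. Severity: minor, optional.

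**What to change.** Keep every planned analysis and add one sentence to C4:

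> *A marker will be called a differential predictor only if a direct test of the difference between its lapse and relapse associations, allowing for both outcomes being measured in the same participants, supports it; otherwise lapse/relapse discordance is reported descriptively.*

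That is sufficient if differences are to be described only. If the sponsor wants to keep the stated ability to identify them, add as secondary analyses:

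- **Aim 1:** a participant-level bootstrap interval for the lapse standardised effect minus the relapse standardised effect, stating which lapse grouping it uses if the median split is invoked.
- **Aim 2:** a joint comparison on one prespecified scale, keeping the full-model terms, including the behavioural task data. If this uses time to lapse, it is a different endpoint from lapse within one week, so it supplements the logistic model and does not replace it.
- **Multiplicity:** adjustment over the ROI, connectivity and state contrasts actually tested.

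The cost is one sentence, or that sentence plus analysis code, on the same data. Fewer differential claims will result. In simulation (n = 58, phi 0.4-0.9, before multiplicity adjustment), Aim 1 power was 80-91% for d of 0 against 0.87, but 32-49% for 0.4 against 0.87 and 13-17% for 0.6 against 0.87. The form of the bootstrap also matters. Under equal effects, a test based on the bootstrap standard error rejected in only 0.3-0.6% at phi 0.9, which is very conservative. The percentile version rejected in 5.9-8.2% at phi 0.4-0.75, which is somewhat liberal, and in 3.0-3.8% at phi 0.9. The choice should be fixed in advance with these limits stated.
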